4.4 What type of research is this?

Biomedical Research
 Clinical trial (FDA regulated)
 Behavioral Research
 Educational Research
 Psychosocial Research
 Oral History
 Other

4.5 Are you conducting this project in pursuit of a personal degree?

@ Yes No

4.7 * Is this human subjects research? (As defined by 32 CFR219) Human subject means a living individual about whom an investigator (whether professional or student) conducting research:
(i) Obtains information or biospecimens through intervention or interaction with the individual, and uses, studies, or analyzes the information or biospecimens; or
(ii) Obtains, uses, studies, analyzes or generates identifiable private information or identifiable biospecimens.

@ Yes No

4.8 * Do you believe this human subjects research is exempt from IRB review?

0 Yes @ No

5.0

Personnel Details

5.1 List any Research Team members without EIRB access that are not previously entered in the protocol:

No records have been added

5.2 Will you have a Research Monitor for this study?

0 Yes
 @ No
 0 N/A

6.0

Data/Specimens

6.1 Does the study involve the use of existing data or specimens only (no interaction with human subjects)?

0 Yes @ No

7.0

Funding and Disclosures

7.1 Source of Funding:

Funding Source	Funding Type	Amount
No records have been added		

Total amount of funding:

7.2 Do you or any other Investigator(s) have a disclosure of a personal interest or financial nature significant with sponsor(s), product(s), instrument(s) and/or company(ies) involved in this study?

0 Yes 0 No

If Yes, complete and attach Conflict of Interest forms for all key personnel

8.0

Study Locations

8.1 Is this a collaborative or multi-site study? (e.g., are there any other institutions involved?)

0 Yes @ No

8.2 Study Facilities and Locations:

Institution	Site Name	Site Role	FWA or DoD Assurance Number	Assurance Expiration Date	Is there an agreement?	IRB Reviewing for Site
Army	Keller Army Community Hospital	Performance site	000029527	10/28 /2025		NMCP IRB

other:

Other Institution Site	Site Role	FWA or DoD Assurance Number	FWA or DoD Expiration Date	Is there an agreement?	IRB Reviewing for Site
No records have been added					

8.3 Are there international sites?

Attach international approval documents, if applicable, when prompted. Note: Ensure local research context has been considered

0 Yes *Gi* No

8.4 Is this an OcoNus (Outside Continental United States) study?

Yes No

Select the area of responsibility:

Have you obtained permission from that area of responsibility? (This is a requirement prior to study approval)

Yes No

9.0

Study Details

9.1 Key Words:

Provide up to 5 key words that identify the broad topic(s) of your study

self-efficacy; musculoskeletal injury; tactical performance; initial-entry training

9.2 Background and Significance:

Include a literature review that describes in detail the rationale for conducting the study. Include descriptions of any preliminary studies and findings that led to the development of the protocol. The background section should clearly support the choice of study variables and explain the basis for the research questions and/or study hypotheses. This section establishes the relevance of the study and explains the applicability of its findings

Since World War I, U.S. Army leaders have faced a challenging conundrum: conduct training tough enough to prepare Soldier for warfare's physical and mental demands without causing so many injuries that units become non-deployable (East, 2013). The steady decline in physical activity levels and increases in overweight and obese adolescents (Center for Disease Control and Prevention /Division of Adolescent, 2020) has continued to widen the physical readiness gap between the general population and military physical demands (Alemany et al., 2021). This disparity increases the difficulty to train physically capable recruits without injuring those who are less fit.

Despite efforts to improve Soldier readiness, as many as 58,400 Soldiers were not capable to deploy in April 2020, which is equivalent to 13 Brigade Combat Teams (Department of the Army, 2020). More than half (31,500) were due to either temporary or long-term physical limitations, including musculoskeletal injuries (MSKIs). MSKIs are the leading cause of nondeployability, lost duty days (LDD), medical encounters, military discharge, and disability (Molloy, Pendergrass, Lee, Chervak, et al., 2020; Roy et al., 2021). In 2018 the U.S. Army spent \$434 million in direct medical costs alone to treat MSKIs (Molloy, Pendergrass, Lee, Chervak, et al., 2020).

Ironically, the leading causes of MSKIs are same activities that leaders deliberately conduct to develop physical resilience: running, foot marching, other physical fitness training activities (besides running) and work-related tasks (Roy et al., 2021). Although physical training results in the highest number of total injuries, obstacle courses and ruck marching have greater injuries per exposure (Lovalekar et al., 2021). Other common causes of MSKIs include overexertion, falls/slips, and accidental injury (Army Public Health Center, 2021).

Lower back injuries are a common occurrence in athletes and sports programs. They are especially common in sports in which athletes train strength and power movements, such as powerlifting and weight lifting (Bengtsson, 2018; Reichel, 2019; Stromback, 2018). Tactical athletes-referring to firefighters, police officers, and military servicemembers- report similar prevalence of low back pain (LBP), often due to heavy equipment worn or carried for their jobs (Roy, 2021). In the US military, musculoskeletal (MSK) injuries are highly prevalent and costly in lost duty days, depleted readiness to deploy, and medical expenses(Grimm, 2019; Teyhen, 2018).

Researchers have identified multiple physical and behavioral MSKI risk factors including prior injury, female gender (Hearn et al., 2021; Kucera et al., 2016), high or low BMI (Lovalekar et al., 2021; Rappole et al., 2017), history of smoking, low aerobic endurance (Molloy, 2016; Rappole et al., 2017),

and (to a lesser extent) muscular strength and endurance (Jones et al., 2017). Unit leaders and military trainers have used these study outcomes to develop injury prevention and training program including physical fitness programs, MSKI risk screening and leader education with mixed results (Canham-Chervak et al., 2015; Lovalekar et al., 2021; Molloy, Pendergrass, Lee, Hauret, et al., 2020; Terry et al., 2018).

These epidemiological and correlational studies summarize the dilemma: Soldiers with prior injury and lower fitness levels tend to get injured (again) while training to improve their physical fitness. It is possible that other modifiable risk factors exist that, if trained, do not carry such high injury risk.

The Army's new mandatory fitness test- Army Combat Fitness Test (ACFT)- is a comprehensive assessment of strength, power, speed, and endurance, and represents a dramatic shift from the previous fitness test that primarily evaluated soldiers' endurance. One event of the ACFT is a three-repetition maximum deadlift. The addition of a required deadlift strength test has raised concern amongst servicemembers and healthcare workers about the risk of injury (Hauschild, 2019; Kind, 2019). The Army doctrine specifies the purpose of testing this event is to evaluate a soldier's lower body and core strength to safely lift heavy equipment, and the graders are instructed to not permit any lumbar flexion during the deadlift. (Army Field Manual 7-22).

Many coaches and physical therapists agree that lumbar flexion should not be permitted during a deadlift (Nolan, 2019; Sjoberg, 2020; Spencer, 2015) however the majority of the research supporting this is based on empirical data derived from biomechanical or cadaver studies (Arjmand, 2005; Cholewicki, 1991; Dolan, 1994; Faber, 2009; Gallagher, 2012; Potvin, 1991; von Arx, 2021; Wade, 2014). There is some debate amongst researchers regarding the importance of avoiding lumbar flexion for injury back injuries during a deadlift (Adams, 1986, 1994; Beach, 2018; Spencer, 2015).

Alberto Bandura (1977) introduced self-efficacy as one's confidence to perform a specific task. In behavioral psychology, this concept helps patients and clinicians establish a therapeutic path by accomplishing individualized, increasingly difficult tasks (Bandura, 1977). Multiple subsequent publications have proposed positive relationships between self-efficacy and self-regulation (Bandura, 1982), performance (Bandura, 1982; Feltz et al., 2008), goal-setting (Brinkman et al., 2020) and motor learning (Beattie et al., 2014).

Performance effects resulting from the messages provided to athletes shouldn't be ignored, and this is referred to as placebo (has a perceived positive effect) or nocebo (has a perceived negative effect (Horvath, 2021). The concept of performance decline after negatively-perceived stimulus has a less robust presence in the literature than placebo effects, though this is evolving. Numerous recent studies have now documented the significant detriments to physical performance when subjects are exposed to negative or potentially threatening information (Cook, 2012; Corsi, 2019; Emadi Andani, 2015; Horcajo, 2019; Jackson, 2005; Pollo, 2012; Zech, 2019).

To our knowledge, there are no longitudinal studies evaluating the risk of injury from deadlifting with a flexed lumbar spine resulting in no clear evidence that a flexed spine is a risk factor for injury. However, it is well documented that information related to potential threat (nocebo) can adversely affect physical performance. Our research aim is to determine if cautionary information about the risk of spine injury harms performance on a maximum strength test compared to a message of spine resiliency. The cautionary education is similar to standard information provided to many servicemembers before the start of an ACFT or a maximum deadlift.

9.3

Objectives/Specific Aims/Research Questions:

Describe the purpose and objective(s) of the study, specific aims, and/or research questions /hypotheses

1. Determine if general self-efficacy is a predictor of injury during Cadet Basic Training(CBT) by performing a Kaplan-Meier Survival Curve of a single self-efficacy assessment (Cadet General Self-Efficacy Assessment) and injury occurrence using the Defense Medical Surveillance System (DMSS), Cadet Illness and Injury Tracking System (CIITS), Armed Forces Health Longitudinal Technology Application (AHLTA) and a follow-up self-reported injury assessment.

1. Independent Variable: Cadet General Self-Efficacy score

2. Dependent Variables: Injury report according to CIITS, AHLTA, DMSS, sick call report or self-reported

2. Determine if task-specific self-efficacy is a predictor of injury during specific CBT events by performing a Kaplan-Meier Survival Curve, a single assessment of cadet task-specific self-efficacy and injury occurrence using DMSS, CIITS, AHLTA and a follow-up self-reported injury assessment.

1. Independent Variable: Cadet Task-Specific Self-Efficacy score

2. Dependent Variables: Injury report according to DMSS or self-reported

3. Determine if general self-efficacy is a predictor of performance during CBT by performing a multivariate regression between a single self-efficacy assessment and multiple measures of performance during CBT including 1) successful completion (pass/fail), 2) Army Combat Fitness Test (ACFT) raw or calculated score, 3) Warrior Competition performance, 4) marksmanship score, 5) written exams, 6) swimming assessment and 7) any other individually graded events.

1. Independent Variable: Cadet General Self-Efficacy score

2. Dependent Variables: performance outcome by event- 1) successful completion (pass/fail), 2) Army Combat Fitness Test (ACFT) score, 3) Warrior Competition performance, 4) marksmanship score, 5) written exams, 6) swimming assessment and 7) any other individually graded events.

4. Determine if task-specific self-efficacy is a predictor of performance during CBT by performing a multivariate regression between a single (or multiple) assessments of cadet task-specific self-efficacy, and multiple measures of performance during CBT including 1) successful completion (pass/fail), 2) Army Combat Fitness Test (ACFT) raw or calculated score, 3) Warrior Competition performance, 4) marksmanship score, 5) written exams, 6) swimming assessment and 7) any other individually graded events.

1. Independent Variable: task-specific self-efficacy scores

2. Dependent Variables: performance outcome by event including 1) successful completion (pass/fail), 2) basic rifle marksmanship qualification score, 3) 12-mile road march outcome (pass/fail), 4) Army Combat Fitness Test (ACFT) score, 5) land navigation score, 6) swimming assessment outcome (pass/fail) and 7) any other individually-graded events.

5. After completing CBT, determine which sources of self-efficacy ((1) enacting mastery experiences, 2) vicarious experiences, 3) verbal persuasion, 4) physiological state, 5) affective state, 6) mental imagery) were the most influential on cadets' self-efficacy throughout CBT specific tasks by conducting a Chi-square test.

1. Independent Variable: reported level of influence of each (6) source of self-efficacy.

2. Dependent Variables: performance outcome by event including 1) successful completion (pass/fail), 2) basic rifle marksmanship qualification score, 3) 12-mile road march outcome (pass/fail), 4) Army Combat Fitness Test (ACFT) score, 5) land navigation score, 6) swimming assessment outcome (pass/fail) and 7) any other individually-graded events.

6. Determine the effect of low back pain education (cautionary vs resiliency) on deadlift performance (weight lifted).

We will analyze this with MDL weight lifted as the dependent variable (one-way ANOVA), with a planned comparison analysis if significant differences are found between groups.

7. Determine the degree of confidence cadets have in their ability to succeed at the MDL both before and after the education and MDL

We will analyze if there is a main effect of time in the pre-to-post self-efficacy scores with a paired t-test. We will use multiple regressions to analyze the impact of self-efficacy scores on MDL performance.

8. Determine the effect of low back pain education (cautionary vs resiliency) on deadlift self-efficacy. We will analyze change scores with one-way ANOVA with planned comparisons between groups if ANOVA is significant.

9. Determine the effect of low back pain education (cautionary vs resiliency) on perceived spine vulnerability on a deadlift.

We will analyze change scores with one-way ANOVA with planned comparisons between groups if ANOVA is significant.

9.4 Study Design:

Describe study design in one to two sentences (e.g., prospective, use of existing records/data /specimens, observational, cross-sectional, interventional, randomized, placebo-controlled, cohort, etc.). Specify the phase - Phase I, II, III, or IV- for FDA-regulated investigational drug research

This study will be a randomized controlled trial with parallel design and 1:1 allocation ratio. We plan to use cluster randomization. We will have three groups- control, cautionary, resiliency (Jackson, 2005).

9.5 Target Population:

Describe the population to whom the study findings will be generalized

U.S. Military Academy Cadets

9.6 Benefit to the DoD:

State how this study will impact or be of benefit to the Department of Defense

Researchers inside and outside of the military have also found that self-efficacy predicts both performance and is negatively correlated with MSKI (Gruber et al., 2009; Samuels et al., 2010). In a study on Navy SEAL training resilience, researchers found that successful graduation was related to physiological markers of resilience (Ledford et al., 2020). However, few studies have investigated the combined effects of physical, behavioral and psychological factors on predicting MSKIs.

Cadet basic training (CBT) at the United States Military Academy (USMA) is a 7-week initial-entry training event that physically and psychologically prepares cadets to become officers. It includes similar training events and physical demands as other initial-entry military courses such as a 12-mile foot march with 35 lbs., physical training including running multiple days per week, weapons familiarization, and basic tactical training. The injury risk factors for cadets attending CBT are similar to trainees attending U.S. Army Basic Combat Training and regular military training even though injury incidence is lower (Hearn et al., 2021). Identifying self-efficacy as an injury risk factor is the first step to designing and implementing injury prevention measures. The purpose of this study is to investigate relationships between performance, MSKI and self-efficacy alone and in combination with other MSKI risk factors in USMA cadets participating in CBT.

There is currently an emphasis in Army Doctrine (FM 7-22) on form/technique for events on the ACFT, especially the maximum deadlift (MDL) and the prevention of lower back injuries. The rationale behind this is due to the perception that breakdowns in form during the deadlift lead to injuries, however, the research does not support this. Specifically, the research is unclear regarding the position of the spine while deadlifting- neutral vs flexed. Our results could impact future DoD publications regarding technique on the MDL and de-emphasize the role of a rounded spine as a safety concern.

The researchers hypothesize that self-efficacy (general and task-specific) will be positively correlated with successful completion and performance and negatively correlated with MSKI risk during CBT. The researchers will also explore the relationship between self-efficacy and other known injury risk factors. Furthermore, we hypothesize that such beliefs about the vulnerability of the spine to injury might contribute to future disabling beliefs about back pain. This research marks an important step in investigating the role of beliefs about the back and readiness.

10.0

Study Procedures, Data Management, and Privacy

10.1 Study Procedures:

Describe step-by-step how the study will be conducted from beginning to end

Phase I: Consent and Self-Efficacy Assessment

All new cadets are eligible to participate in this study and will receive verbal and written study description during the first or second week of cadet basic training. Immediately after consenting to participate, they will complete the study demographic data information and the Cadet Basic Training Projective Performance

Invent01y, which assesses self-efficacy measured prospectively via questionnaire on a 10-point Likert scale from 1 (no confidence) to 10 (fully confident) for overall performance during cadet basic training, marksmanship/live fire training, mock marching 12 miles, land navigation, swimming, and the Army Combat Fitness Test. It will also assess for any recent injuries and whether the injury is currently hindering them.

Phase 2: Injury Surveillance During Cadet Basic Training

These researchers will monitor the Cadet Injury and Illness Tracking System (CIITS), Armed Forces Health Longitudinal Technology Application (AHLTA) and the Defense Medical Surveillance System (DMSS) up to weekly to track injuries for the duration and for up to 9 weeks afterwards. They will classify injuries as by diagnosis, region, and impact on training ("not injured" (1), "injured-not limited" (2), "injured-modified training" (3) and "injured-limited" (4)). Cadets will initially be defaulted as "not injured" (1). They will also complete the Single Assessment Numeric Evaluation (SANE), rating their current ability level on a scale of 0-100% with regards to their injury.

Phase 3: Maximum Deadlift and Low Back Pain Education

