Cadet Demographics: Age, gender, height, weight, USMA Preparatory School attendance, intended athletics participation, intended USMA performance

Injury Questionnaire: Recent injury information (within last year), still effecting performance, and Single Assessment Numeric Evaluation (SANE), and after-cadet basic training injury presence, region, and limiting classification

Self-Efficacy: Overall Cadet Basic Training performance, marksmanship, buddy team live fire, swimming 150 yards, ruck marching (load carriage), ACFT, deadlift, land navigation

Maximum Deadlift (MDL) performance: Measured by the amount of weight successfully lifted during the ACFT.

Reported Self-Efficacy Source: Measured on the post-CBT survey using Qualtrics. The cadets will rank-order commonly cited sources of self-efficacy from most to least influential. The options will include commonly-cited self-efficacy sources: physiological state, previous experiences, affective state, mental imagery, vicarious experiences, and verbal persuasion.

10.3 At any point in the study, will you request, use, or access health information in any form, including

verbal, hard copy and electronic?

Yes No

10.4 Review the definitions below and respond to the following two questions. If you are not sure of the answers, email [contact] for assistance. The Military Health System (MHS) is defined as all DoD health plans and DoD health care providers that are organized under the management authority of, or in the case of covered individual providers, assigned to or employed by, the Defense Health Agency (DHA), the Army, the Navy, or the Air Force. MHS workforce members are employees, volunteers, trainees, and other persons whose conduct, in the performance of work for the MHS, is under the direct control of the MHS, whether or not they are paid by the MHS. MHS business associates are persons or entities that provide a service to the MHS and require protected health information (PHI) to provide the service.

Are you an MHS workforce member?

Yes, I am an MHS workforce member
 No, I am not an MHS workforce member

Are you an MHS business associate?

Yes, I am an MHS business associate
 No, I am not an MHS business associate

10.5 Have you consulted with an MHS data expert to determine the data elements required for your study?

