4. Determine if task-specific self-efficacy is a predictor of performance during CBT by performing a multivariate regression between a single (or multiple) assessments of cadet task-specific self-efficacy, and multiple

measures of performance during CBT including 1) successful completion (pass/fail), 2) Army Combat Fitness Test (ACFT) raw or calculated score, 3) Warrior Competition performance, 4) marksmanship score, 5) written exams, 6) swimming assessment and 7) any other individually graded events.

1. Independent Variable: task-specific self-efficacy scores by event
2. Dependent Variables: performance outcome by event- 1) successful completion (pass/fail), 2) Army Combat Fitness Test (ACFT) score, 3) Warrior Competition performance, 4) marksmanship score, 5) written exams, 6) swimming assessment and 7) any other individually graded events.

5. After completing CBT, determine which sources of self-efficacy (1) enacting mastery experiences, 2) vicarious experiences, 3) verbal persuasion, 4) physiological state, 5) affective state, 6) mental imagery) were the most influential on cadets' self-efficacy throughout CBT specific tasks including 1) successful completion (pass/fail), 2) Army Combat Fitness Test (ACFT) raw or calculated score, 3) Warrior Competition performance, 4) marksmanship score, 5) written exams, 6) swimming assessment and 7) any other individually graded events by conducting a Chi-square test.

1. Independent Variable: task-specific events 1) successful completion (pass/fail), 2) Army Combat Fitness Test (ACFT) score, 3) Warrior Competition performance, 4) marksmanship score, 5) written exams, 6) swimming assessment and 7) any other individually graded events.
2. Dependent Variables: reported level of influence of each (6) source of self-efficacy.

6. Determine the effect of low back pain education (cautionary vs resiliency) on deadlift performance (weight lifted).

We will analyze this with MDL weight lifted as the dependent variable (one-way ANOVA), with a planned comparison analysis if significant differences are found between groups.

7. Determine the degree of confidence cadets have in their ability to succeed at the MDL both before and after the education and MDL

We will analyze if there is a main effect of time in the pre-to-post self-efficacy scores with a paired t-test. We will use multiple regressions to analyze the impact of self-efficacy scores on MDL performance.

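### Objective 5 in 9.3 relates six-place source ranks to event performance by Chi-square test alone, which discards order and cuts the graded scores; 11.6 describes a different analysis

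*Combined protocol and SAP*

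**What the plan says.** Section 9.3 item 5 names one method: it will find which sources "were the most influential on cadets' self-efficacy throughout CBT specific tasks by conducting a Chi-square test". Its variable list begins "Independent Variable: reported level of influence of each (6) source of self-efficacy". The dependent variables are performance by event and mix two kinds of outcome. Marksmanship, ACFT and land navigation are scores ("4) Army Combat Fitness Test (ACFT) score, 5) land navigation score"), while completion, the 12-mile march and swimming are pass/fail.

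Section 10.2 gives the form of the source measure: "The cadets will rank-order commonly cited sources of self-efficacy from most to least influential". Each cadet therefore supplies ranks 1 to 6.

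Section 11.6 item 5 keeps the same test ("any other individually graded events by conducting a Chi-square test") but swaps the roles. It has "Independent Variable: task-specific events 1) successful completion (pass/fail), 2) Army Combat Fitness Test (ACFT) score" and so on, with the influence of each source as the dependent variable. Its event list adds the Warrior Competition and written exams and does not name land navigation or the road march.

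Neither section gives a table layout, score bands, the form of Chi-square test, or an effect size or power for this objective. Section 11.1 does not mention it.

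**The concern.** An ordinary (Pearson) Chi-square test works on a contingency table of unordered categories. Under the 9.3 variable list, two kinds of information are thrown away. A graded score has to be banded at cut points chosen later, and the six rank positions are treated as if they had no order. The result carries no direction or size, and it can change with the cut. Objectives 3 and 4 already plan regression for the same kind of performance outcome, and no reason is given for switching here.

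If the link between crediting a source and performing well is weak, much of the power to see it is lost for no gain. In addition, the two sections do not describe the same analysis, so an analyst could follow either and claim to be on plan.

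**Working it through.** **Inputs.** The test and variable roles come from 9.3 and 11.6 (item 5 in each), the rank scale from 10.2, and the number of cadets from 11.5. Assumed, because the plan is silent: two-sided 5%, ranks spread evenly over 1 to 6, roughly normal scores, a linear link with correlation r, and one source at a time with one row per cadet.

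**The plan's own figure.** The 969 in 11.5 reproduces as a three-group one-way ANOVA with Cohen's f = 0.10 at 5%: power 0.801. It belongs to the deadlift comparison (Objective 6). It serves here only as a plausible number of cadets and says nothing about the power of Objective 5.

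**Full-scale comparator.** With a normal score, the Spearman correlation is about 0.977r, where 0.977 = √(3/π). At r = 0.092 it is 0.0899. The test statistic has mean about √969 × 0.0899 / √(1 − 0.0899²) = 2.81, so power is Φ(2.81 − 1.96) = Φ(0.85) = 0.80.

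**Chi-square noncentrality.** For small r, λ ≈ n r² × (share of score information kept) × (share of rank information kept).
- n r² = 969 × 0.092² = 8.20.
- Score share: median split 2/π = 0.637; thirds 0.793; quarters 0.861.
- Rank share: all six positions 1; ranked first against the rest (2.5² × 0.2)/(35/12) = 0.429; top three against bottom three 1.5²/(35/12) = 0.771.

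| Table | λ | df | Power |
|---|---|---|---|
| Six ranks × median split | 8.20 × 0.637 = 5.22 | 5 | 0.38 |
| Six ranks × thirds | 8.20 × 0.793 = 6.50 | 10 | 0.35 |
| Six ranks × quarters | 8.20 × 0.861 = 7.06 | 15 | 0.32 |
| Ranked first × median split | 8.20 × 0.637 × 0.429 = 2.24 | 1 | 0.32 |
| Top three × median split | 8.20 × 0.637 × 0.771 = 4.03 | 1 | 0.52 |

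Simulation of the same five tables gave 0.37, 0.36, 0.30, 0.30 and 0.52 against 0.80 for Spearman, a loss of about 28 to 50 points. With no association, all six tests rejected in 4.4% to 5.7% of runs. The loss is therefore lost information and does not come from a wrong error rate. With 600 cadets, and r raised to about 0.12 to keep 80% power, the loss is 29 to 49 points.

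**Other strengths of link, n = 969.**

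| r | Loss by formula (points) | Loss by simulation (points) |
|---|---|---|
| 0.05 | 14 to 22 | 15 to 22 |
| 0.092 | 28 to 48 | 28 to 50 |
| 0.15 | 9 to 31 | 9 to 32 |
| 0.20 | 1 to 2 (about 10 for ranked first) | about 1 (10 for ranked first) |

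A different model (latent bivariate normal, six rank classes, 2 to 6 score bands) agrees in order of size. It loses 18 to 21 points at a latent correlation of 0.05, 42 to 54 at 0.10, 19 to 31 at 0.15, 2 to 5 at 0.20 and about 0 at 0.30.

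**Pass/fail events.** No outcome is cut, so only rank order is lost. For a one-degree-of-freedom trend test at 80% power, λ = (1.96 + 0.84)² ≈ 7.85. The same λ on 5 df gives power 0.555, a loss of about 24.5 points. With assumed pass rates of 80% to 90%, the unordered test had 54% to 56%.

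**The stated question.** Asking which source ranks highest compares six dependent ranks within each cadet. If the ranks were pooled into a 6 × 6 source-by-rank table, the Pearson statistic under no preference would behave like 6/5 times a Chi-square on 25 df. The 5% critical value is 37.65, and P(χ² on 25 df > 37.65 × 5/6 = 31.4) is about 0.18. A simulation with 500 cadets gave about 16%.

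**The case against.** The strongest reply is that this rests on one of two readings. The stated aim is to compare sources. With the roles as 11.6 has them, the analysis could be a table of counts, events by sources, in which no score is used and the loss computed above does not arise. Section 10.1 Phase 5 fits that reading, since cadets answer about sources of confidence during specific events. This stands. The power argument applies to 9.3 as written, and the conflict with 11.6 is part of the point.

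A reader might infer that the plan loses a fixed 30 to 50 points, or that real links would mostly be missed. The documents do not support that. They give no effect size or table for this objective, and that range belongs to a link explaining under 1% of variance (0.092² = 0.0085). By r = 0.20 the loss is nearly gone for most tables. The assumed linear link also favours the ordered method.

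A reader might also infer that every outcome is forced into bands. Three of the six outcomes named in 9.3 are already binary. Nor does the plan say which Chi-square form is meant: a linear trend test is itself a Chi-square test and keeps the order.

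Finally, a slope of score on rank does not say which source was most influential. That is correct, so the slope cannot be the whole remedy.

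**Conclusion.** The point holds for 9.3 item 5. With scores as outcomes and ranks as predictors, an ordinary Chi-square test needs unstated cuts, ignores order and gives no direction or size. Its power cost with 969 cadets depends on the strength of the link: about 28 to 50 points near r = 0.09, 15 to 22 at 0.05, 9 to 32 at 0.15, and about 1 for most tables at 0.20. These figures assume the unordered Pearson form, a linear link, roughly normal scores and evenly spread ranks. None of the settings examined favoured the Chi-square test. For pass/fail events the loss is smaller and comes from rank order alone.

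The documents do not support calling the test invalid when each source is tabulated separately with one row per cadet, because its error rate is then correct. They also do not support treating 11.6 item 5 as the same analysis.

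Objective 5 is not the randomized comparison, so this is a change that should be made but does not threaten the trial's main result.

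**What to change.** 1. Reconcile 9.3 item 5 with 11.6 item 5: one set of variable roles, one list of events, and a statement of whether the ranking is given once or per event.
2. Where performance is the outcome, replace the Chi-square test. For graded scores, use Spearman correlation or linear regression of the full-scale score on the ordered rank, and report the estimate with a confidence interval. For pass/fail events, use logistic regression on the ordered rank or a trend test.
3. Keep the question of which source was most influential as a separate within-cadet comparison of the six ranks, for example a Friedman test or a rank-ordered model.

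The cost is wording in two sections, with no new data, cadets or procedures. There are two downsides. A one-degree-of-freedom trend is less sensitive to a non-monotone pattern, which can be shown descriptively. Testing each source against each event also gives many tests: six sources by the six events named in 9.3 is already 36. These should be labelled exploratory or adjusted for multiplicity.
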